4.2.6. Derivations of Safety Endpoints

Baseline definition for all safety endpoints is given in Section 5.3. Change from baseline is calculated as on-treatment value minus the baseline value. Handling of time points is described in Section 5.4.

4.2.6.1. Treatment-emergent Adverse Event

A treatment-emergent adverse event (TEAE) is defined as any AE that begins or worsens on or after the date of the first dose of IP through 28 days after the last dose of IP for subjects who have completed the study or have discontinued early by the time of database cut, or on or after the date of the first dose of IP for subjects who are ongoing at the time of database cut.

If the treatment-emergent status of an AE is unclear due to a missing/incomplete start date, it will be defined as a TEAE, unless shown otherwise by data. Date imputation rules for partially missing AE start dates are described in Section 16.2.

Relationship to IP is based on the investigator's causality judgment; that is, a drug-related AE is an AE indicated by the investigator to have a suspected relationship to IP.

4.3. Stratification, Randomization, and Blinding

At Visit 2, subjects who meet entry criteria will be randomized using a permuted block randomization in parallel 1:1 (102 subjects per group) to receive either APR 30 BID or identically-appearing placebo BID for the 12-week Placebo-controlled Treatment Phase, using a centralized Interactive Response Technology (IRT). Eligible subjects will be stratified according to sex, history of uveitis, and region (Japan and Other).

This study will be conducted as a double-blind study for the Placebo-controlled Treatment Phase. During the Active Treatment Phase (Weeks 12 to 64), the IP will remain blinded, to prevent study personnel and subjects from knowing the IP assignment in the Placebo-controlled Phase.

To maintain the blind regarding the initial treatment assignment, all subjects will receive dose titration cards at Visit 9. Although only subjects initially randomized to placebo will be dose titrated during their first week of the Active Treatment Phase, all subjects entering the Active Treatment Phase will receive identically-appearing titration/treatment cards.

Data analyses and reporting will be performed after all subjects have completed Week 12/Visit 9 or have discontinued early (the 12-week database). After medical/scientific review has been completed, protocol violations/deviations have been identified, and the data have been declared final and complete, the 12-week database will be extracted and restricted with the corresponding external data files in the appropriate location in the data repository. For 12-week database lock, Celgene personnel who have access to the unblinded data are not to discuss or make materials available that would unblind individual subjects data to the personnel involved in the study conduct. Blinding to treatment assignment will be maintained at all study sites prior to the Week 68 database lock.

4.4. Sample Size Determination

The sample size estimation is based on the consideration from the results of the Phase 2 study CC-10004-BCT-001. A 2-sided t-test at a 0.05 significance level will have 90% power to detect a treatment difference of 66 in the AUC of oral ulcer counts from Day 1 through Week 12 (AUC₈₅ of placebo – drug = 66), the primary efficacy endpoint, when the sample size in each group is 102, assuming a common standard deviation of 144.

5. GENERAL STATISTICAL CONSIDERATIONS

5.1. Reporting Conventions

Summary statistics for continuous variables include sample size (n), mean, standard deviation (SD), median, minimum, the 25th (Q1) and 75th (Q3) percentiles, and maximum. All mean and median values will be formatted to one more decimal place than the measured value. SD values will be formatted to two more decimal places than the measured value. Minimum and maximum values will be presented to the same number of decimal places as the measured value. Frequency summary for categorical variables includes number and percentage. All percentages will be rounded to one decimal place. Number and percentage values will be presented as xx (xx.x%). All analysis and summary tables will have the population sample size for each treatment group in the column heading. P-values (2-sided) will be presented with 4 decimal places. All laboratory data will be reported using standard international (SI) units.

5.2. Analysis Periods

For the purposes of data analysis and reporting, 2 analysis periods are defined as follows, unless otherwise defined for a specific tabulation. Data analysis and reporting for a specific analysis period will include all data measured or collected (based on date of measurement or date of specimen collection, as appropriate) during that analysis period.

- Placebo-controlled period:

This period starts on the date of the first dose of IP, and stops

- on the date the first dose of apremilast is administered at the Week 12 visit (Visit 9), or
- on the date of the last study visit (including the ET Visit and the Observational Follow-up Visit; i.e., all data after the start date will be included) for efficacy analyses, or 28 days after the last dose of IP or the date of death (if applicable), whichever comes first, for safety analyses, for whom IP is not dispensed at Week 12

The start day is exclusive and the stop day is inclusive for efficacy, and safety analyses based on laboratory, vital signs, and weight. For AE analyses, the start day is inclusive, and the stop day under the first bullet is exclusive and the stop day under the second bullet is inclusive.

- Apremilast-exposure period:

This period starts

- on the date the first dose of apremilast is administered for subjects who are randomized to an apremilast dose group, or
- on the date the first dose of apremilast is administered at the Week 12 (Visit 9) for subjects who were originally randomized to placebo and switched to the APR 30 BID group,

and this period stops

- For efficacy analyses, on the date of the last study visit (including the ET visit and the Observational Follow-up Visit; i.e., all data after the start date of the apremilast-exposure period will be included), or
- For safety analysis, 28 days after the last dose of apremilast for subjects who have completed the study or have discontinued early, or the date of death (if applicable), whichever comes first.

The start day is exclusive and stop date is inclusive for efficacy analyses, and safety analyses of laboratory, vital signs, and weight. For AE analyses, both the start date and stop date are inclusive.

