### **6.6.1. Adverse Events**

The time frames for recording all AEs are indicated in [Section 5](#). It should be noted that during the first 64 weeks of the study worsening of a subject's BD should be considered as worsening of the disease under study, and should not be captured as an AE. Worsening of disease will be captured on a separate BD activity page in the eCRF that lists each of the BD manifestations.

Worsening of a subject's BD will be captured on the AE eCRF for subjects who continue in the optional Open-label Extension Phase after Week 64.

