2. INTRODUCTION

This statistical analysis plan (SAP) describes the analyses and data presentations for Celgene's protocol CC-10004-BCT-002 "A Phase 3, Multicenter, Randomized, Double-blind, Placebo-controlled Parallel Group Study, followed by an Active-Treatment Phase to Evaluate the Efficacy and Safety of Apremilast (CC-10004) in the Treatment of Subjects with Active Behçet's Disease," Amendment 1 and Amendment 1.1 DE, which were issued on 02 FEB 2016 and 05 JUL 2017 (for German sites only), respectively. It contains definitions of analysis populations, derived variables and statistical methods for the analysis of efficacy and safety.

Throughout this SAP, the treatment arms will be referred to as the 30 mg twice daily (BID) group and the placebo group. The purpose of the SAP is to ensure the credibility of the study findings by pre-specifying the statistical approaches for the analyses of study data prior to database lock and the data analyses. This SAP will be finalized and signed prior to the clinical database lock for the first analysis (at 12 weeks).

These analyses include:

- Week 12 data analyses: clinical efficacy and safety analyses based on a database cut at Week 12/Visit 9 after all subjects have completed Week 12/Visit 9 or have discontinued early at or prior to Week 12, including Early Termination and Observational Follow-up visits (referred as the 12-week database). The treatment comparisons during Placebo-controlled Treatment Phase and the safety analysis for the Placebo-controlled period will be based on this database lock;
- Analyses of efficacy up to Week 28 and safety with at least 100 subjects with at least 1 year of apremilast exposure (referred as the second database);
- Week 68 analyses: clinical efficacy and safety analyses when all subjects have completed the Active Treatment Phase and/or 4-week Posttreatment Observational Follow-up Phase or have discontinued early;

In addition, for German sites only:

- Analyses for the optional Open-label Extension Phase for subjects from German sites who choose to enter the optional Open-label Extension Phase after completing the Active Treatment Phase.

All statistical analyses detailed in this SAP will be conducted using *SAS*® 9.2 or higher.

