| Visit 14 | Week 64 | Week 64 | 449 | 408 | 
For subjects entering Active Treatment Phase but not entering optional Open-label Extension Phase:
 
 1) 1 day prior to date of Observational Follow-up Visit if Observational Follow-up Visit performed or 2) ET visit if performed or 3) Date of APR treatment discontinuation if subjects discontinue study and have no Observational Follow-up visits, whichever is later. 
For subjects from German sites entering the optional Open-label Extension Phase, the end day is when the IP is administered at Visit 14
 |

APR = Apremilast; ET = Early termination.

The time points for analyses of efficacy data will be assigned according to visit window scheme in [Table 2](#) which are set up as the continuous and mutually exclusive, from midpoint to midpoint between each successive part of scheduled visits or otherwise specified.

The time points for summaries of safety data (laboratory parameters, vital signs, and weight) will be assigned as defined above for both placebo-controlled and apremilast-exposure period for subjects who are randomized as APR30 BID; and for placebo-control period only (through Week 12) for placebo subjects. For all placebo subjects who switch to the APR 30 BID group at Week 12, safety data within apremilast-exposure period will be mapped to reflect the Study Days relative to the first dose of apremilast (see [Table 3](#) below). In addition, safety analysis on the end of treatment will be included, which is defined as the last visit among all the scheduled and unscheduled visits and, if applicable, the Early Termination visit, all within the same analysis period. The baseline visit and the Observational Follow-up Visit are not included in the derivation of the end-of-treatment value.

Table 3: Mapping of Study Weeks for Placebo Subjects who Switched Treatment in Summary of Safety Data over Time

| Visit | Week | Mapped Analysis Time Point | Target APR Day | Start (APR Day) | End (APR Day) |
|----------|---------|----------------------------|----------------|-----------------|--|
| Visit 9 | Week 12 | Baseline | 1 | | Last measure prior to First APR Dose Date(\leq 1 APR day) |
| Visit 10 | Week 16 | Week 4 | 29 | 2 | 71 |
| Visit 11 | Week 28 | Week 16 | 113 | 72 | 155 |
| Visit 12 | Week 40 | Week 28 | 197 | 156 | 239 |
| Visit 13 | Week 52 | Week 40 | 281 | 240 | 323 |
| Visit 14 | Week 64 | Week 52 | 365 | 324 | 407 |

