9. STUDY TREATMENTS AND EXTENT OF EXPOSURE

9.1. Treatment Duration

Treatment duration will be summarized by treatment group for the placebo-controlled period using the safety population, and for the apremilast-exposure period using the apremilast subjects as treated population. Subjects whose treatments are switched to active therapy will have the following treatment group designation: Placebo/APR 30 BID in the apremilast-exposure period. A subject data listing of study drug administration will be provided.

Treatment duration (in weeks) is calculated as (the date of the last dose of IP – the date of the first dose of IP + 1) / 7 during each period and rounded to one decimal place. Summary statistics for subject years, treatment duration (in weeks), as well as a frequency summary of treatment duration categories (e.g., \geq 1 day, < 2 weeks, \geq 2 to < 6 weeks, etc.), will be provided.

The specific definitions of the first and last dose dates for the Placebo-controlled and Apremilast-exposure periods are given below:

- Placebo-controlled period:
 - First dose date: The date of the first dose of IP.
 - Last dose date:
 - 1 day before the date of first dose of apremilast administered at the Week 12/Visit 9, or
 - The date of the last dose of IP in the study for subjects who discontinue the study on or prior to Week 12/Visit 9.
- Apremilast-exposure period:
 - First dose:
 - The date the first dose of apremilast is administered for subjects who receive apremilast at randomization, or
 - The date the first dose of apremilast is administered at the Week 12 (Visit 9) for subjects who originally received placebo during the Placebo-controlled Treatment Phase and switched to the APR 30 BID group when entering Active Treatment Phase.
 - Last dose date:
 - The date of the last dose of apremilast during Active Treatment Phase for subjects who have either completed or discontinued Active Treatment Phase by the time of database lock or study close, or
 - The latest date out of scheduled visit dates, AE event dates or study drug administration dates for treatment ongoing subjects at time of database lock (ie, the second database in Section 2).

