11. SAFETY ANALYSES

11.1. General Approaches to Safety Analyses

Safety analyses will be performed for both the placebo-controlled and apremilast-exposure periods (see Section 5.2), based on the safety population and the apremilast subjects as treated population respectively. Summary tables during the placebo-controlled period are presented by treatment group, Placebo and 30 mg BID. During the apremilast-exposure period, data are presented by treatment sequence, i.e., Placebo/30 mg BID, 30 mg BID as Initiated, and a total column of 30 mg BID as Treated.

Unless otherwise specified, the analyses of AEs and marked abnormalities (laboratory parameters and vital signs) for both the placebo-controlled and apremilast-exposure periods will include the subject incidence rate (i.e. percentage [%] used in a frequency summary), which is defined as the number of subjects with the specific event divided by the number of subjects included in the analysis. Subjects with multiple occurrences of the specific event in the specific analysis period will be counted only once in the numerator.

To account for the different exposure to the IP, AEs and laboratory marked abnormalities will also be analyzed using exposure-adjusted incidence rate (EAIR) per 100 subject-years as defined below:

- The EAIR per 100 subject-years is defined as 100 times the number of subjects with the specific event divided by the total exposure time (in years) among subjects included in the analysis. Subjects with multiple occurrences of the specific event in the specific analysis period will be counted only once in the numerator. The exposure time for a subject without the specific event is the treatment duration, whereas the exposure time for a subject with the specific event is the treatment duration up to the start date (inclusive) of the first occurrence of the specific event. The total exposure time in years is calculated by dividing the sum of exposure time in days over all subjects included in the analysis by 365.25. The EAIR per 100 subject-years is interpreted as the expected number of subjects with at least one occurrence of the specific event per 100 subject-years of exposure to the study drug.

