Summaries of vital signs, weight, and laboratory parameters over time (e.g., summary statistics of observed value and changes from baseline and shifts from baseline to post-baseline time points in terms of normal/abnormal or grade) will be provided. In summaries for a post-baseline time point, subjects who have both values at baseline and at the time point will be included; for end of period and shifts from baseline to the end of period and to the worst post-baseline value, subjects who have a baseline value and at least one post-baseline value will be included.

Safety data collected during the optional Open-Label Extension Phase will be listed.

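### For German-site extension subjects, the SAP leaves the safety event window open past Week 64 while the exposure denominator stops there, and the listing-only intent is not written into the definitions

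*SAP*

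**What the plan says.** **Event window.** For safety, SAP 5.2 stops the apremilast-exposure period "28 days after the last dose of apremilast for subjects who have completed the study or have discontinued early", or at death if sooner. SAP 4.2.6.1 uses the same 28-day limit for treatment-emergent adverse events (TEAEs) in subjects who have completed or left the study. Otherwise it counts any event "on or after the date of the first dose of IP for subjects who are ongoing at the time of database cut". Protocol 6.11 places study completion for a subject who enters the extension at the end of the extension.

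**Exposure.** SAP 9.1 sets the last dose date of the same period at "The date of the last dose of apremilast during Active Treatment Phase for subjects who have either completed or discontinued Active Treatment Phase". SAP 11.1 carries this into the exposure-adjusted incidence rate (EAIR): "The exposure time for a subject without the specific event is the treatment duration".

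**Visit windows.** In SAP 5.4, Table 2, the Week 64 window for German-site extension subjects closes so that "the end day is when the IP is administered at Visit 14".

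**Extension data.** SAP 11.1 states: "Safety data collected during the optional Open-Label Extension Phase will be listed". Protocol 10.7 says the same. SAP 2 names as a separate item "Analyses for the optional Open-label Extension Phase for subjects from German sites".

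**Recording of Behçet's disease.** Through Week 64, protocol 6.6.1 keeps worsening of the disease off the adverse event form; protocol 11.1 excepts serious events. Afterwards worsening is "captured on the AE eCRF for subjects who continue in the optional Open-label Extension Phase after Week 64".

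**The concern.** Numerator and denominator of the apremilast-exposure rates come from different sections, and for extension subjects those sections end at different times. A programmer who builds the period and TEAE flags from SAP 5.2 and 4.2.6.1 will flag extension events. The exposure variable built from SAP 9.1 will hold no extension time.

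The change in recording at Week 64 makes this more than an arithmetic mismatch. Non-serious flares from a few subjects in one country would appear in the apremilast tables as adverse events, with nothing comparable recorded earlier or elsewhere. The tables at stake are the long-term ones: TEAE incidence, EAIR and the exposure-interval summaries at the Week 68 lock, and at the second lock for anyone already past Visit 14.

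**Working it through.** The plan states no figure on this point, so the check sets the rules side by side and then sizes the mismatch under assumptions.

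**1. Where each rule ends for an extension subject**

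| SAP section | Controls | End |
|---|---|---|
| 5.2 | Period for safety data | 28 days after the last extension dose; no stop if still in the extension |
| 4.2.6.1 | TEAE status | The same; no upper limit if ongoing at the cut |
| 9.1 | Treatment duration, hence EAIR exposure | Last Active Treatment Phase dose, about Day 449 |
| 5.4, Table 2 | Assigning assessments to visits | Visit 14 dose, about Day 449 |

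There are two materially different end points: about Week 64, and an end in or beyond the extension. By Visit 27 (Day 1457) they lie (1457 − 449)/7 = 144 weeks apart.

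**2. What admits an event to the tables.** SAP 11.2 lists every adverse event regardless of period and restricts the summaries to TEAEs. Being listed therefore does not keep an event out of a table. TEAE status and the period flag decide, and neither is capped at Visit 14.

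**3. Size for an ordinary, infrequent event.** The design gives 102 subjects per group, with 64 weeks of apremilast in one and 52 in the other.
- If all complete: (102 × 64 + 102 × 52)/52.18 = 226.8 subject-years.
- With assumed losses (factor 0.95 in both groups and a further 0.90 for placebo subjects who never switch): 102 × 0.95 × 64/52.18 + 102 × 0.90 × 0.95 × 52/52.18 = 118.9 + 86.9 = 205.8 subject-years.

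At a constant rate, inflation is roughly uncounted extension time divided by counted time. The documents give no number of entrants; 2 to 20 entrants with 0.5 to 2 years each are assumed.
- Low: 2 × 0.5/226.8 = 0.4%.
- Middle: 10 × 1/226.8 = 4.4%, or 10 × 1/205.8 = 4.9%.
- High: 20 × 2/205.8 = 19%.

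Allowing for censoring at the first event (constant hazard, all 204 complete), a true 2.00 per 100 subject-years becomes 2.01 to 2.34, and a true 10.0 becomes 10.04 to 11.51.

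**4. Size for non-serious worsening.** Assume no adverse event record before Week 64 and 0.5 first events per year in the extension.
- Low: 2 × (1 − e^(−0.25)) = 0.44 events; 0.44/226.8 = 0.2 per 100 subject-years.
- High: 20 × (1 − e^(−1)) = 12.64 events; 12.64/226.8 = 5.6 per 100.

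Adding the missing exposure in the high case gives 12.64/(226.8 + 12.64/0.5) = 5.0 per 100. Correcting the denominator alone would leave the artefact almost intact, because its source is the recording rule.

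**5. Interval tables (SAP 11.2.2).** The numerator counts a subject in any interval where an event started. The denominator needs treatment duration above the interval's lower bound. A placebo subject who switches at Day 85 and takes the last Active Treatment Phase dose on Day 448 has (448 − 85 + 1)/7 = 52.0 weeks and is not in the interval above 52 weeks; one more day gives 52.1 weeks and includes the subject. That subject's extension events would nevertheless fall in the intervals above 52 and above 64 weeks. For subjects on apremilast from the start, a last dose on Day 449 to 456 gives 64.1 to 65.1 weeks, so the last interval holds at most about 8 days each.

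**The case against.** The best reply is that the plan already settles the matter. SAP 11.1 and protocol 10.7 provide for listing extension safety data, SAP 6 puts extension disposition in its own listing, and SAP 2 treats the extension as a separate German-site analysis. SAP 5.2 also opens by allowing a particular table to define its period differently, which could let the listing rule override the general window. The open-ended branch of SAP 4.2.6.1 has a natural use at the second database, where most subjects are still on treatment. On this reading no extension event enters a rate and the effect is zero.

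Much of this stands as evidence of intent. It does not close the gap. The listing sentence does not say that extension data are only listed, and no adverse event table invokes the reservation in SAP 5.2. SAP 9.1 and Table 2 each carry an explicit limit for this situation; the two sections that define the event flags carry none.

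It is also fair that, for every subject, the SAP counts events to 28 days after the last dose but exposure only to the last dose. The last interval is therefore sparse and unstable in any case. For extension subjects, though, the excess can run to years.

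**Conclusion.** The point holds as an inconsistency between definitions. Followed literally, SAP 5.2 and 4.2.6.1 admit extension events, including non-serious worsening of Behçet's disease, to tables whose exposure ends at about Week 64. Listing only is the likely intent but is not what those sections say. Under the assumed entrants and durations, EAIRs of infrequent events rise by about 0.4% to 19%, and the late interval tables are the most exposed. If few German subjects enter, the effect is small. The primary endpoint, the ranked tests and the placebo-controlled safety comparison are untouched.

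Three stronger readings are not supported:
- **Three conflicting end points.** SAP 9.1 and Table 2 agree at about Week 64, and Table 2 assigns visits rather than counting events.
- **Planned pooling of extension data.** The interval above 64 weeks in SAP 11.2.2 does not show this, since a last dose on Day 449 already exceeds 64 weeks.
- **A forecast rate of thousands per 100 subject-years in that interval.** Ten events over ten extension subjects with 7 days each would give 10/(10 × 7/365.25), about 5,200 per 100. But SAP 11.2.2 includes every subject above the bound. With an assumed 40 others at 7 days, it is 10/(50 × 7/365.25), about 1,040. Neither is a prediction; they show only that the interval cannot carry such events.

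**What to change.** In SAP 5.2 and 4.2.6.1, add that for subjects who enter the Open-label Extension the apremilast-exposure period and the TEAE window for summary tables end at the first extension dose at Visit 14. The stop day should be inclusive for laboratory values, vital signs and weight, and exclusive for adverse events. This mirrors the SAP 5.2 rule at Week 12 and keeps the Visit 14 assessments; stopping the day before would lose them and would disagree with Table 2. In SAP 11.1, state that events from that dose onward are listed only.

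Extending SAP 9.1 exposure into the extension is the weaker alternative, because it would still mix two recording rules for Behçet's disease in one rate.

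The cost is minor reprogramming of the period flag, with no new data. Extension subjects would have no 28-day tail in the summary tables, but those events remain visible in the listing. The change should be made before the Week 68 lock, and before the second lock if any subject will by then have passed Visit 14.
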